1.0 What is the condition or intervention to be studied?

We are studying the use of platelet-rich plasma (PRP) injections for the treatment of gluteus medius tendinopathy, which is often referred to as Greater Trochanteric Pain Syndrome (GTPS). This condition is characterized by pain in the lateral aspect of the hip that is aggravated by side lying, stair climbing, and walking. The underlying pathophysiology is tendinosis or partial thickness tear of the abductor muscles of the hip (most commonly the gluteus medius). This condition is identified by history, physical exam, and confirmatory MRI or ultrasound of the hip.

2.0 What is/are the research question(s)/specific aim(s)? Pose very specific questions that can be addressed within the proposed design of the study. Prioritize them in order of importance.

Does injecting autologous platelet-rich plasma into a gluteus medius tendon with tendinopathy and partial tear result in greater improvement in pain and function than does injecting whole blood alone?

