3.0 What is/are the hypothesis(es)?

An injection of platelet-rich plasma into the affected gluteus medius tendon will improve pain and function related to this condition with greater efficacy than does injecting whole blood alone.

4.0 Identify and define the primary outcome and when the outcome will be measured. If measuring change in post-operative function is the most important, that will be your primary outcome.

The primary outcomes are improvement in pain, function, and patient satisfaction following platelet-rich plasma or whole blood injection. These outcome measures will be measured via the Numerical Rating Scale for Pain, Non-Arthritic Hip Score, Veterans RAND 12-Item Health Survey, and a 10-cm visual analog scale (VAS) for patient satisfaction which will range from “very dissatisfied” to “extremely satisfied.”

The primary outcome measures will be recorded on day of injection, then 6 weeks, 3 months, 6 months, 9 months, and 1 year post-injection

5.0 Identify and define the secondary outcome(s) and when they will be measured (list additional goals one at a time with their corresponding outcomes).

Secondary outcomes include the Forward Step-down Test (FSD) and patient reported pain during resisted side-lying hip abduction. Patient reported pain during the FSD and resisted side-lying abduction will be measured using a 10-cm visual analog scale (VAS). Other secondary outcomes include any untoward side-effects including increased pain, bleeding, and

infection.

The FSD and resisted side-lying hip abduction outcome measures will be recorded on day of injection, then 3 months, 6 months, and 1 year post-injection.

All other secondary outcome measures will be recorded on day of injection, then 6 weeks, 3 months, 6 months, 9 months, and 1 year post-injection

BACKGROUND - Be sure to answer each question individually

1.0 Explain why these research questions are being asked:

There is no current prospective literature regarding PRP or whole blood injections for the treatment of gluteus medius tendinopathy despite having evidence that these treatments may positively affect tendon healing. It is unknown whether injection with PRP for tendinopathy is more efficacious than injection with whole blood alone. This study may demonstrate efficacy of PRP injections for the treatment of gluteus medius tendinopathy, which would offer patients a potential treatment option prior to the consideration of surgery.

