4. Knee position: if the knee of the tested limb moves medially in the frontal plane and the tibial tuberosity crossed an imaginary vertical line positioned directly over the second toe of the tested foot, 1 point will be given. If the knee moves medially and the tibial tuberosity crosses an imaginary vertical line positioned directly over the medial border of the tested foot, 2 points will be given.
5. Maintenance of a steady unilateral stance: if the patient had to support body weight on the non-tested limb, or the foot of the tested limb moves during testing, 1 point will be given.

A total score of 0 or 1 will be classified as good movement quality, a total score of 2 or 3 will be classified as moderate movement quality, and a total score of 4 or more will be classified as poor movement quality.³⁹

The FSD movements will be recorded neck-down and stored on Citrix ShareFile for future evaluation by a single, blinded investigator.

The patient's pain while performing the FSD will be collected using a Visual Analog Scale.

The patient's pain while performing resisted, side lying hip abduction will also be collected. The patient will be asked to lie on the asymptomatic side, with the hip in approximately 30° of abduction and 5° of extension with their toes pointed downward. One hand of the examiner will be placed on the iliac crest and the other hand will be placed on the lateral portion of the knee. The patient will then be asked to maximally abduct the hip against manual resistance.

Their pain will be recorded following this test using the Visual Analog Scale.

The Forward Step-down Test will be performed pre-injection as well as 3 months, 6 months, and 1 year post-injection. All remaining data will be collected pre-injection and following injection 6 weeks, 3 months, 6 months, 9 months, and 1 year. Questionnaires will be completed either on paper at the time of a normally scheduled office visit, mailed to the study subject in a pre-paid envelope, or online.

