All patients will be required to participate in a structured home exercise program beginning 2 weeks post-injection. In order to ensure standardization for this, all patients will receive two individualized physical therapy sessions with a physical therapist for instruction on these exercises, which will focus primarily on strengthening the hip abductors. Patients will also receive a handout with specific exercise instructions as a guide for their home exercise program. They will also be asked to complete an exercise log in order to help assess

compliance with their home exercise program.

Follow-up study questionnaires on pain, function, and satisfaction will be administered as previously stated.

At 6 months post-injection, the participants who do not report satisfactory improvement will be unblinded, and those who were in the whole blood group will be offered an opportunity to receive a PRP injection for their gluteus medius tendinopathy.

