## **Data Analysis Plan**

Descriptive analyses of the patient population will include reporting means (with standard deviations) for continuous variables and frequencies (with percentages) for categorical or discrete variables. Independent samples t-test (or non-parametric equivalent) will be used to assess the differences in continuous variables among the two study groups, while chi-square or Fisher's exact test will assess the association between categorical or discrete variables against the study groups. Odds ratio and their 95% confidence intervals will be calculated to measure the strength of that association.

We powered our study to demonstrate an MCID of 15 points in the non-arthritic hip pain score (NAHS) with estimated standard deviation of  $\pm 20$  points. Using that estimate, it was determined that sample sizes of 30 patients in each group achieves 86% power using a two-way repeated measures analysis of variance model with 4 follow-up points and statistical significance set to alpha equal to 0.01. To account for a potential loss-to-follow-up rate of 20%, we plan to increase enrollment for each treatment by 6 patients.

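### The SAP's four unnamed follow-up points for NAHS must, on a plain reading, include data from after the 6-month unblinding and PRP offer, which no longer compare PRP with whole blood alone.

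*Protocol*

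**What the plan says.** - **Question and hypothesis.** The protocol's research question (2.0) asks whether PRP gives "greater improvement in pain and function than does injecting whole blood alone". The hypothesis (3.0) is that PRP works "with greater efficacy than does injecting whole blood alone".
- **Schedule.** Protocol 4.0: "The primary outcome measures will be recorded on day of injection, then 6 weeks, 3 months, 6 months, 9 months, and 1 year post-injection". That is five post-injection visits for every measure listed as primary, including NAHS.
- **Month 6.** Under Interventions and Observations, 1.0, at 6 months "the participants who do not report satisfactory improvement will be unblinded, and those who were in the whole blood group will be offered" a PRP injection. Unblinding applies to unsatisfied participants in both arms; the PRP offer applies to the whole-blood arm only.
- **Data collection.** Besides paper forms at office visits, the same section allows questionnaires to be "mailed to the study subject in a pre-paid envelope, or online".
- **Analysis.** The SAP's Data Analysis Plan bases power for NAHS on a "two-way repeated measures analysis of variance model with 4 follow-up points", with 30 per group, a 15-point difference, SD 20 and alpha 0.01. The points are not named. A general sentence says that a t-test or non-parametric equivalent "will be used to assess the differences in continuous variables among the two study groups".
- **Attrition.** "To account for a potential loss-to-follow-up rate of 20%, we plan to increase enrollment for each treatment by 6 patients", giving 36 per arm.

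Neither document names a primary time point or says how data after unblinding, or after a PRP injection in the whole-blood arm, are to be analysed.

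**The concern.** Three of the five follow-up visits fall at or before month 6, so any choice of four includes month 9 or month 12. By then some whole-blood participants may have had PRP, and some participants in both arms know their allocation. Analysed as randomised, those visits estimate PRP against whole blood followed by optional PRP. That is not the comparison with whole blood alone that the protocol poses.

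Crossover runs one way and depends on outcome. If PRP works and is taken up, the late difference shrinks, and a null result cannot separate PRP being no better from controls having improved on PRP. Knowledge of allocation may also shift self-reported scores in either direction. With the visits unnamed, the question that the trial answers depends on a choice that could be made after the data are seen.

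**Working it through.** **1. Visit count.** By month 6: 6 weeks, 3 months, 6 months = 3. After month 6: 9 and 12 months = 2. Four follow-up points therefore include at least 4 − 3 = 1 late visit, and possibly both.

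**2. Reproducing the stated power.** SAP inputs: difference d = 15, SD 20, n = 30 per group, alpha 0.01, m = 4. Assumptions not in the documents: two-sided test, group main effect, compound symmetry with correlation r, and a constant 15-point difference.

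- Variance of a patient's mean over m visits: V = 400 × (1 + (m − 1)r)/m.
- Normal approximation: power = Φ(d/√(2V/n) − 2.576).
- Check by noncentral F: F(1, 2n − 2) with noncentrality n·d²/(2V).

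At m = 4 and r = 0.5, V = 400 × 2.5/4 = 250. Then 15/√(500/30) = 3.674, and Φ(3.674 − 2.576) = 0.864, the SAP's figure. With the F test, r = 0.453 gives 0.864.

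**3. Three visits through month 6.** At r = 0.5, V = 400 × 2/3 = 266.7. Then 15/√(533.3/30) = 3.558, and Φ(0.982) = 0.837. The F test at r = 0.453 gives 0.832.

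**4. Dilution if four visits are kept.** Let L be the number of late visits, c the fraction of the whole-blood arm crossing over, and g the share of the 15 points that they gain. The documents give neither c nor g. If crossover is unrelated to score, the average difference is d = 15 × (4 − L·c·g)/4. For c = 0.2, g = 1, L = 1, d = 14.25. The last column is a simulation (F test, r = 0.453) in which the lowest month-6 scorers in the whole-blood arm cross over.

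| c | g | L | d | Power, unrelated to score | Power, lowest scorers |
|---|---|---|---|---|---|
| 0.2 | 1 | 1 | 14.25 | 0.820 | 0.837 |
| 0.2 | 1 | 2 | 13.50 | 0.768 | 0.802 |
| 0.2 | 0.5 | 1 | 14.625 | 0.843 | 0.852 |
| 0.2 | 0.5 | 2 | 14.25 | 0.820 | 0.837 |
| 0.6 | 1 | 2 | 10.50 | 0.498 | 0.561 |

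The last row is a deliberate extreme.

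**5. If the tested effect is group-by-time, with baseline as a level.** With differences 0, 15, 15, 15, 15, r = 0.655 reproduces 0.864. Baseline plus the three visits through month 6 gives 0.868. With 20% crossover, power is 0.834 (one late visit) or 0.787 (two) at full gain, and 0.845 or 0.821 at half gain.

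**6. Sensitivity to r (group effect).** At r = 0.7, three visits give 0.749 (normal) or 0.719 (F), and four undiluted visits give 0.765 or 0.735.

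**7. After attrition.** 36 × 0.8 = 28.8 per arm. With 28 or 29 analysed per arm, three visits give 0.805 or 0.822 (normal) and 0.799 or 0.816 (F). Four undiluted visits give 0.835 or 0.850 (normal) and 0.833 or 0.849 (F).

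**The case against.** - **Baseline may be the fourth point.** The phrase about four points occurs only in the power sentence, and a repeated-measures ANOVA often has baseline as a time level. Baseline, 6 weeks, 3 and 6 months make four and stop at the unblinding. The power figure cannot rule this out, because group-by-time over those four points also gives 0.864, at a correlation of about 0.652. This stands as a possible reading, but the text says follow-up points, and baseline is not one. On that reading the 9- and 12-month measurements, which the protocol lists as primary, fall outside the powered model and are covered at most by the general t-test sentence. Using all five follow-ups instead would bring in both late visits. Under every reading the SAP has to name its visits.
- **A report of dissatisfaction must precede the unblinding that it triggers, so the 6-month data are clean.** This is likely, but not assured: a participant can report dissatisfaction while the mailed or online NAHS form is still outstanding, and no order is stated.
- **Power hardly changes.** This is correct at 20% crossover with one late visit: 0.82–0.84 at full gain and 0.84–0.85 at half gain, against 0.83–0.84 for three clean visits. Dilution also pulls towards no difference, so by itself it does not create a false positive. The case for change rests on the question answered.
- **Analysis by randomised arm to 12 months is legitimate.** It is, provided the SAP says that this is the question. At present the protocol states a different one.

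**Conclusion.** The concern holds and must be fixed. On the plain reading, the powered NAHS analysis includes one or two visits at which the control condition may have become whole blood plus PRP and blinding is partly lost, with no rule for those data. This follows from the visit count and needs no assumption beyond reading follow-up as post-injection.

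The effect on power is secondary and rests on an assumed correlation, tested effect, crossover rate and gain. At 20% crossover, the power of the four-visit group-effect test falls from 0.864 to between 0.77 and 0.85, depending on gain, the number of late visits and who crosses over. Higher crossover lowers it further. The size of any bias from unblinding cannot be estimated from the documents.

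**What to change.** Leave the 6-month PRP offer as it is and change the analysis wording:

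1. Define the primary NAHS comparison as the between-group effect in the repeated-measures analysis over 6 weeks, 3 months and 6 months, as randomised. Use the same visits for the other measures that protocol 4.0 lists as primary.
2. Require the 6-month questionnaires to be completed before any unblinding.
3. Report 9 and 12 months as secondary, by randomised arm, labelled as post-unblinding and post-crossover, with the number who crossed over.
4. Restate power with its correlation and tested effect: about 0.83–0.84 at 30 per group under the assumptions above, and 0.72–0.75 if the correlation is 0.7.

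If the sponsor prefers to keep month 9 or 12 in the confirmatory analysis, the SAP should name PRP versus whole blood followed by optional PRP as the question, and state the expected dilution.

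**Cost.** Protocol and SAP wording only, with no new visits or data. Months 9 and 12 leave the confirmatory claim. For the group effect, stated power falls by about three points at 30 analysed per group, and to about 0.80–0.82 at the planned 20% loss. Restoring 0.864 needs 32 (normal) or 33 (F) analysed per group, that is, at most 36 − 32 = 4 or 36 − 33 = 3 losses per arm. If group-by-time with baseline is the tested effect, there is no power cost (0.868).

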## **Sample Size Analysis**

Proposed analysis: Two-way repeated measures analysis of variance

Alpha level: 0.01

Beta or power level: 0.864

Number of groups being compared: 2

Effect size or change expected between groups: 15-point change between groups

Resulting number per group: 30

Total sample size required: 72

## **Data Analysis Plan**

Descriptive analyses of the patient population will include reporting means (with standard deviations) for continuous variables and frequencies (with percentages) for categorical or discrete variables. Independent samples t-test (or non-parametric equivalent) will be used to assess the differences in continuous variables among the two study groups, while chi-square or Fisher's exact test will assess the association between categorical or discrete variables against the study groups. Odds ratio and their 95% confidence intervals will be calculated to measure the strength of that association.

We powered our study to demonstrate an MCID of 15 points in the non-arthritic hip pain score (NAHS) with estimated standard deviation of  $\pm 20$  points. Using that estimate, it was determined that sample sizes of 30 patients in each group achieves 86% power using a two-way repeated measures analysis of variance model with 4 follow-up points and statistical significance set to alpha equal to 0.01. To account for a potential loss-to-follow-up rate of 20%, we plan to increase enrollment for each treatment by 6 patients.

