1.0 Be specific and describe the Interventions or Observations that will be part of this research project. **Include a detailed description of the treatment arms, if applicable.**

General information related to the patient, including age, sex, duration of symptoms, etc., will be obtained from patient charts. Numerical Rating Scale for Pain, Non-Arthritic Hip Score, and Visual Analog Scale (VAS) for patient satisfaction will be collected. The VAS will also be used to measure the patient's pain during resisted side-lying abduction and during a Forward Step Down (FSD) test. The quality of the movement during the FSD test will also be assessed.

For the Forward Step-down Test (FSD), the patient will stand on a 22-cm step. Patients will then be asked to step down with their asymptomatic limb by bending only the knee on their

symptomatic side until the heel of the asymptomatic side touches the floor, without weight bearing on the heel. Once their heels reach the floor, they will be asked to immediately re-extend the knee on the symptomatic limb to return to the starting position. While performing this movement, the patients will be asked to keep their trunk straight with their hands on their waist. Once they are familiar with the movements, they will be asked to perform 5 consecutive FSD movements.

After the 5 consecutive trials of the FSD test, the examiner will assess the quality of the movement as either good movement quality, moderate movement quality, or poor movement quality based on the following 5 criteria:

1. Arm strategy: if the patient uses an arm strategy to recover balance, 1 point will be given. Because subjects will be instructed to keep their hands on their waist, removing their hands from their waist will be interpreted as a strategy to recover balance.
2. Trunk movement: if the patient leans the trunk to either side, this will be interpreted as recovering balance, 1 point will be given.
3. Pelvic plane: if 1 side of the pelvis is rotated in the transverse plane or elevated in the frontal plane compared with the other side, 1 point will be given.

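### Forward Step-down movement quality is an ordered three-level secondary outcome, but the only SAP rule that fits it ignores the order and does not say which odds ratio is reported

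*SAP*

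**What the plan says.** **Protocol, section 5.0 (secondary outcomes).** "Secondary outcomes include the Forward Step-down Test (FSD) and patient reported pain during resisted side-lying hip abduction". These measures "will be recorded on day of injection, then 3 months, 6 months, and 1 year post-injection", which gives one baseline and three follow-up assessments.

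**Protocol, Interventions and Observations, 1.0.** After five repetitions, "the examiner will assess the quality of the movement as either good movement quality, moderate movement quality, or poor movement quality". Five criteria carry at most 1, 1, 1, 2 and 1 points. A score of 0 or 1 is good, 2 or 3 is moderate, and "a total score of 4 or more will be classified as poor movement quality". The movement is also filmed and the recording is kept "for future evaluation by a single, blinded investigator". The same section says that at 6 months participants without satisfactory improvement are unblinded, and that those given whole blood are then offered PRP.

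**SAP, Data Analysis Plan.** Continuous variables get a t-test or a non-parametric equivalent. For the rest, chi-square or Fisher's exact test "will assess the association between categorical or discrete variables against the study groups", followed by odds ratios with 95% confidence intervals. The FSD is not mentioned. No ordinal method, reference level, dichotomy, use of baseline or handling of repeated visits is given for it.

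**The concern.** The grades are ordered by construction, and the hypothesis (Protocol, section 3.0) is directional: PRP should improve function more than whole blood. A two-degree-of-freedom chi-square on a 2 by 3 table gives the same answer however the columns are arranged, so it spends part of its power on patterns that the hypothesis does not predict. Fisher's exact test on such a table also takes no account of the order.

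Two choices are also left until after the data are seen. A 2 by 3 table yields several odds ratios, and the SAP does not pick one. The protocol describes both an examiner's grade and a later blinded video evaluation, and neither document says which is analysed. The examiner is not stated to be blinded, and some participants know their allocation before the 1-year test.

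**Working it through.** **1. The plan's own power figure.** The SAP gives 0.864 for the Non-Arthritic Hip Score (NAHS): 30 per group, difference 15, SD 20, alpha 0.01, four follow-up points. The within-patient correlation is not stated; assume 0.5 and a two-sided test.
- SD of the mean of four measures: 20 × √[(1 + 3 × 0.5)/4] = 15.81.
- Standard error of the difference: 15.81 × √(2/30) = 4.08.
- Power: Φ(15/4.08 − 2.576) = Φ(1.10) = 0.864.

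The figure reproduces. It concerns NAHS only; neither document gives a power for FSD.

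**2. The scale.** The maximum score is 1 + 1 + 1 + 2 + 1 = 6, cut at 0–1, 2–3 and 4 or more. The result is three ordered levels.

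**3. Power of an unordered against an ordinal test.** Assumptions not in the documents: the control distribution, the common odds ratio, two-sided testing, and the alpha for secondary outcomes (0.05 and 0.01 are both shown). Setting: 30 per arm at one visit, no covariates.
- Shift: the odds of being at or better than each cut in the PRP arm equal OR × the control odds. For control 20/40/40% (good/moderate/poor) and OR 3, the cumulative odds 0.25 and 1.5 become 0.75 and 4.5. The PRP arm is then 42.9/39.0/18.2%.
- Unordered test: X² = Σ(O − E)²/E on 2 df.
- Ordinal test: tie-corrected rank-sum, z = [W − n(N + 1)/2]/√V, with V = (n²/12) × [(N + 1) − Σ(t³ − t)/(N(N − 1))]. It stands in for the unadjusted proportional-odds test, to which it is close.
- With 30 per arm there are 496 possible results per arm, so all 496² = 246,016 pairs can be weighted by their multinomial probabilities. A simulation of 20,000 trials per setting agrees to within one percentage point.

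Power for control 20/40/40%:

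| Common OR | Chi-square, 0.05 | Ordinal, 0.05 | Chi-square, 0.01 | Ordinal, 0.01 |
|---|---|---|---|---|
| 2 | 0.230 | 0.298 | 0.081 | 0.119 |
| 3 | 0.510 | 0.617 | 0.265 | 0.359 |
| 4 | 0.717 | 0.809 | 0.468 | 0.584 |

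Gain of the ordinal test in percentage points, for OR 2 / 3 / 4:

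| Control split (%) | Alpha 0.05 | Alpha 0.01 |
|---|---|---|
| 20/40/40 | 6.8 / 10.7 / 9.2 | 3.7 / 9.4 / 11.6 |
| 33/33/33 | 6.9 / 10.9 / 9.7 | 3.7 / 9.2 / 11.4 |
| 30/50/20 | 6.7 / 10.9 / 10.0 | 3.8 / 9.8 / 12.3 |
| 10/30/60 | 6.8 / 10.9 / 9.5 | 3.9 / 9.5 / 11.8 |
| 50/35/15 | 6.8 / 11.3 / 11.4 | 3.9 / 9.7 / 13.0 |
| 25/45/30 | 6.8 / 10.7 / 9.5 | 3.7 / 9.5 / 11.9 |

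The range is about 7 to 11 points at 0.05 and 4 to 13 at 0.01. With no effect, both tests stay close to or below their nominal level, so the gain is not bought with extra false positives.

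**4. A non-ordered difference.** For 20/60/20% against 40/20/40% the ranking reverses: chi-square 0.84, ordinal 0.06 at alpha 0.05.

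**5. Which odds ratio?** From the table with control 20/40/40% and common OR 3:
- good against the rest: 0.75/0.25 = 3.0
- good or moderate against poor: 4.5/1.5 = 3.0
- good against poor: (42.9/18.2)/(20/40) = 4.7
- moderate against poor: (39.0/18.2)/(40/40) = 2.1
- good against moderate: (42.9/39.0)/(20/40) = 2.2

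**The case against.** The strongest reply is that the SAP makes no choice of test for FSD at all. Its rule is general, sits in a paragraph that opens with description of the patient population, and may be meant mainly for baseline characteristics. This stands: a reader might infer that the SAP expressly tests FSD by chi-square, and it does not. The rule reaches FSD only because nothing else fits. Since the rule also covers discrete variables, it would probably take in the 0 to 6 score too. If it was not meant for FSD, movement quality has no stated analysis, and the remedy is the same.

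Three further objections also stand.
- The power comparison assumes an ordered shift, which favours the ordinal test, and step 4 shows the reverse case. That case needs treatment to increase both good and poor grades, which is not the trial's hypothesis.
- At a common odds ratio of 2 both tests have little power (0.23 against 0.30), so the choice of test would rescue little.
- The video evaluation by a blinded investigator may already be how the final grade is meant to be assigned. The protocol does not say that the FSD examiner learns the allocation. Bias from an unblinded rating is a risk that the text leaves open, not something it shows.

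**Conclusion.** The concern holds in limited form. FSD movement quality is ordered, the only applicable SAP rule ignores that order, and the rule leaves the effect measure open. Under an ordered shift with 30 per arm, the cost is about 7 to 11 points of power at alpha 0.05 and 4 to 13 at 0.01. These figures rest on assumed control splits and common odds ratios of 2 to 4, at a single visit without baseline adjustment.

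The documents do not support several stronger readings that a reader might draw:
- *The odds ratio is undefined for three levels.* It is unspecified: several exist, and in the worked example they run from 2.1 to 4.7.
- *Chi-square is weaker whatever the pattern.* It is weaker for an ordered shift only.
- *The sample size has too little power for FSD.* The 86% belongs to NAHS, no power is claimed for FSD, and the total of 72 is unaffected.
- *FSD is the main functional outcome among the secondaries.* The protocol does not rank them, and it places function, with NAHS, among the primary outcomes.

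Severity is low: this is a cheap improvement to the analysis of one secondary outcome.

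**What to change.** Add an FSD paragraph to the SAP, before any unblinded data are examined:
- **Model.** In place of chi-square or Fisher's exact, use a proportional-odds model on the three ordered levels with treatment group and baseline FSD as covariates.
- **Visits.** Choose one and state it: a single named follow-up visit, or all of 3, 6 and 12 months with a random patient effect. If 12 months is included, say how data are handled after the 6-month unblinding and offer of PRP.
- **Effect measure.** Report the common odds ratio with its 95% confidence interval, and state the direction (for example, odds of a better grade on PRP).
- **Rating.** Name the blinded video rating as the one analysed, at baseline and follow-up. The examiner's grade can be listed descriptively.

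The cost is SAP wording. The assessments and the blinded video evaluation are already planned, and no patients are added. The one downside is that the proportional-odds assumption must be checked. The SAP should say how, and should state that the frequencies of all three grades will be shown by arm, so that a non-ordered pattern would be visible.

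### The SAP plans no adjustment for baseline NAHS, which is already collected; adding it to the averaged group contrast would probably gain power at almost no cost

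*SAP*

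**What the plan says.** The SAP's Sample Size Analysis reads "Proposed analysis: Two-way repeated measures analysis of variance" and "Effect size or change expected between groups: 15-point change between groups". The Data Analysis Plan adds that "sample sizes of 30 patients in each group achieves 86% power using a two-way repeated measures analysis of variance model with 4 follow-up points", with "statistical significance set to alpha equal to 0.01", 15 NAHS points as the MCID and an estimated standard deviation of 20 points.

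Neither section names the effect to be tested (group or group-by-time), the four visits, a within-patient correlation or any covariate. Nor do they say whether baseline NAHS is a time level, is subtracted or is left out. The other comparative methods listed (t-test or non-parametric equivalent, chi-square or Fisher's exact test, odds ratios) are unadjusted.

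Baseline NAHS will be available. Protocol item 4.0 on the primary outcome says "The primary outcome measures will be recorded on day of injection, then 6 weeks, 3 months, 6 months, 9 months, and 1 year post-injection". Interventions and Observations agrees: "All remaining data will be collected pre-injection and following injection 6 weeks, 3 months, 6 months, 9 months, and 1 year". That is one baseline and five follow-ups, against four in the power statement.

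**The concern.** A baseline measure of the primary scale usually predicts later scores. If it is left out of the model, that predictable variation stays in the error term. If it is simply subtracted, power depends heavily on the correlation between visits and can fall below that of ignoring baseline. The SAP gives no correlation, so it cannot show which of these two unadjusted routes is better. Using baseline as a covariate largely avoids the choice. At stake is power the trial could have from data it already collects.

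The unnamed effect matters for the same reason: the stated 86% fits one reading of a two-way repeated-measures ANOVA and not others.

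**Working it through.** **Inputs.** From the SAP: n = 30 per group, difference 15, SD 20 (variance S = 400), alpha 0.01, four follow-up points. Assumed: two-sided test; SD 20 refers to scores; the full 15 points at every visit; complete data; equal correlation r between all visits, baseline included, shown at 0.3, 0.5 and 0.7.

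**Formulas**, for the mean of k post-injection visits, per-patient variance:

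- post-injection only: Vp = S(1 + (k−1)r)/k
- change from baseline: Vc = Vp + S(1 − 2r)
- baseline as covariate: Va = Vp − S·r²

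The noncentrality is 15/√(2V/30). The unadjusted tests use a noncentral t with 58 df. The adjusted test uses 57 df, with the variance multiplied by 1 + F/58 and averaged over F ~ F(1, 58), which allows for chance baseline imbalance.

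**The SAP's own figure.** With k = 4 and r = 0.5, Vp = 400 × 2.5/4 = 250. The noncentrality is 15/√(500/30) = 3.674, and Φ(3.674 − 2.576) = 0.8640, which is the stated 0.864. The t distribution gives 0.840. A single visit gives 0.629 by the same normal approximation. The group-by-time tests tried at r = 0.5, with baseline as a time level, give 0.49 to 0.67. The four-visit mean is therefore the likely basis, but r = 0.5 is inferred.

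**The same contrast, three uses of baseline (k = 4):**

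| r | Vp | Vc | Va | post-only | change | adjusted |
|---|---|---|---|---|---|---|
| 0.3 | 190 | 350 | 154 | 93.5% | 67.0% | 97.3% |
| 0.5 | 250 | 250 | 150 | 84.0% | 84.0% | 97.6% |
| 0.7 | 310 | 150 | 114 | 73.5% | 97.9% | 99.6% |

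Post-only loses power as r rises and change loses power as r falls. The adjusted contrast is highest in each row.

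**When baseline predicts poorly.** Hold r = 0.5 among three follow-ups, so that Vp = 400 × 2/3 = 266.7 and post-only power is 81.0%. With a separate baseline correlation rb, Va = 266.7 − 400·rb². Adjusted power is 83.0% at rb = 0.2, equals post-only near rb = 0.11, and is 80.2% at rb = 0. With four visits, an uninformative baseline takes 84.0% to 83.1%.

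**When the effect starts late.** Take effects of 0, 15 and 15 at 6 weeks, 3 months and 6 months, with r = 0.5.

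- Three-visit mean: the average effect is 10, giving 62.2% adjusted and 39.3% post-only.
- 6-month difference alone: 74.3% adjusted (Va = 400 − 100 = 300) and 59.7% unadjusted.
- Omnibus group-by-time with baseline as a level: the four differences 0, 0, 15, 15 have mean 7.5 and squared deviations summing to 4 × 56.25 = 225. The noncentrality is 15 × 225/(400 × 0.5) = 16.875 on 3 and 174 df, giving 82.8%.

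Within each averaged or single-visit contrast adjustment still helps, but here the omnibus test beats both adjusted contrasts. The ordering reverses for a constant effect: with baseline and four follow-ups at r = 0.5, group-by-time has 65.4%, against 97.6% for the adjusted mean.

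**The case against.** The best defence is that nothing here makes the planned comparison invalid. In a randomised trial an unadjusted analysis is unbiased, and under the inferred inputs the trial already has about 84% power at the strict alpha of 0.01. The wording about follow-up points, together with the reproduction of 0.864, also suggests that a post-injection mean was intended. All of this stands. The missing names are, taken alone, missing detail; what makes the point worth acting on is a better use of data already in hand.

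The size of the gain rests on values the documents do not give: the correlations, the meaning of SD 20 and a constant effect from 6 weeks. That also stands, so the gain is conditional. The figures are for an analysis of each patient's visit mean with complete data, which only approximates a mixed model with missing visits. At 28 per arm, three visits and correlation 0.5, the comparison is 94.4% adjusted against 77.5% post-only, so the ordering survives a somewhat smaller sample.

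A reader might infer that the stated 86% is wrong, or that baseline adjustment beats every repeated-measures test. The documents support neither. The first figure reproduces, and the late-onset case contradicts the second.

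A reader might also bring in the statement that "At 6 months post-injection, the participants who do not report satisfactory improvement will be unblinded" and the PRP offer that follows. How the 9- and 12-month scores enter after that is a separate question about what is being estimated. It adds no weight here.

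**Conclusion.** The point holds as a conditional, nearly free improvement that should be made. For the averaged NAHS contrast that reproduces the SAP's power, baseline adjustment raises power from 84.0% to 97.6% at an assumed correlation of 0.5. Over 0.3 to 0.7 it stays at 97.3% or above, while the post-only test falls to 73.5% at one end and the change score to 67.0% at the other. This assumes 30 evaluable patients per arm, 15 points at every visit, SD 20 of scores and equal correlations. With a correlation of 0.5 among three follow-ups, the gain disappears below a baseline correlation of about 0.11; the most that can be lost is about 1 point. The conclusion does not extend to the choice between an averaged contrast and an omnibus test, which depends on the expected time course. Confidence is medium, because the correlations are undocumented.

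**What to change.** In the Data Analysis Plan, make the primary NAHS analysis a linear mixed model of post-injection scores with baseline NAHS as a covariate, terms for treatment, visit and treatment-by-visit, and a small-sample degrees-of-freedom method. Prespecify the one treatment contrast to be tested and the visits it covers, reconciling the four points in the power statement with the five scheduled follow-ups. Choose that contrast for the expected time course; if benefit is expected late, compare its power with the omnibus test before settling.

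Restate power for the chosen contrast, giving the assumed correlations (baseline to follow-up and among follow-ups), the assumed time course and whether SD 20 refers to scores or to change.

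The cost is SAP wording and a rerun power calculation, with no added patients, visits or data, and about 1 point of power or less if baseline proves uninformative.
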